**Not Related:**

There is no reasonable possibility that the study product caused or contributed to the AE (e.g., the AE does not follow a reasonable temporal sequence from study product administration), or can be reasonably explained by other factors (e.g., the disease under study, concurrent diseases, or concomitant medications).

### **7.2.3. Adverse Event Recording Guidelines**

To improve the quality and consistency of safety data, recording of AEs/SAEs in the CRF should follow these general guidelines:

- Standard English medical terminology should be used rather than colloquial expressions or abbreviations.
- Whenever possible, the AE should be evaluated and reported as a diagnosis rather than as individual signs or symptoms. If a definitive diagnosis is not possible, the individual signs and symptoms should be recorded.
- If an AE requires a surgical or diagnostic procedure, the illness leading to the procedure should be recorded as the AE, not the procedure itself.
- For deaths, whenever possible, the underlying or immediate cause of death should be reported as an SAE. Death should be recorded as an outcome of an SAE, not an SAE in itself.

### **7.3. Serious Adverse Event Reporting**

The Investigator and Sponsor are responsible for determining whether an event should be classified as serious. If in the opinion of the Investigator, the AE meets the criteria of an SAE, the SAE is to be reported to the Sponsor or Sponsor's designee. All SAEs, regardless of causality, must be reported. SAEs must be reported from the time the Informed Consent Form (ICF) is signed until 30 days after the last dose of study drug. SAEs considered related to study drug that occur after the specified Follow-up period should also be reported.

For expedited reporting purposes, SAEs assessed as Related or Possibly Related by the Investigator will be considered as "Related" events, while those assessed as Unlikely Related or Not Related will be considered as "Not related" events.

#### **7.3.1. Study Sponsor Notification by Investigator**

Any SAEs, regardless of causality, must be reported to the Sponsor or Sponsor's designee within 24 hours of the Investigator or any site staff's knowledge of the event.

Within 24 hours after receipt of additional relevant information, the Investigator must provide Follow-up information on the SAE along with any additional relevant documentation (e.g., test results, physician narrative, discharge summary, autopsy findings) that will assist in the understanding of the event.

#### **7.3.2. Institutional Review Board/Ethics Committee Notification**

The Investigator must report all SAEs (including Follow-up information) to the IRB/EC in accordance with IRB/EC requirements. Copies of each report and documentation of IRB/EC notification and receipt will be kept in the site's Regulatory Binder.

#### **7.3.3. Serious Adverse Event Follow-up**

The Investigator must respond to all queries received from the Sponsor and must submit Follow-up reports for all SAEs to the Sponsor or Sponsor's designee regarding the subject's subsequent course. All SAEs must be followed until:

- The SAE is Resolved, or
- Stabilized (e.g., in the case of persistent impairment), or
- Subject death, or
- Subject is lost to follow-up

SAE Follow-up information should be recorded in the source documents and SAE/CRF forms as applicable.

### **7.4. Pregnancy Reporting**

Should a female subject or female partner of a male subject become pregnant at any time during the study, the Investigator must notify the Sponsor within 24 hours after learning about the pregnancy. The Sponsor will request Follow-up information regarding the course of the pregnancy and its outcome. Voluntary consent must be obtained from a female subject or female partner of a male subject (and/or legally authorized representative if the subject is

mentally incompetent or physically incapacitated) before any pregnancy-related Follow-up is obtained.

Pregnancy, in and of itself, is not considered an AE, unless there is suspicion that the study product may have interfered with the effectiveness of a contraceptive medication or method. However, any pregnancy complication or elective termination of a pregnancy for medical reasons will be recorded as an AE or SAE and will be followed accordingly. A spontaneous abortion is considered to be an SAE.

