**Table 7: Timepoints for Assessing Sufficient Anticoagulation and for Ciraparantag/Placebo Dosing (Day 3 or Day 4)**

[figure not shown]
Cohort	Anticoagulant	Timepoint for assessing sufficient anticoagulation	For sufficiently anticoagulated subjects, timepoint for ciraparantag/placebo dose
1	Edoxaban	2.75 hours after Day 3 or Day 4 edoxaban dose	3 hours after the last edoxaban dose
2	Apixaban	3.75 hours after Day 3 or Day 4 apixaban dose	4 hours after the last apixaban dose
3	Rivaroxaban	3.75 hours after Day 3 or Day 4 rivaroxaban dose	4 hours after the last rivaroxaban dose

Subjects in all cohorts who receive ciraparantag/PBO will remain domiciled in the clinical study unit for 5 days after dosing (i.e., through Day 8 or Day 9). Evaluations on the day following ciraparantag/PBO dosing will include WBCT, PK, and safety assessments (including testing for prothrombotic markers). On subsequent days, follow-up safety assessments (including testing for prothrombotic markers) will continue. Any subject with WBCT on the day following ciraparantag/PBO dosing that is  $>120\%$  of BL (based on the coagulometer) or  $>110\%$  of BL (based on the manual method) will have both WBCT measurements repeated on subsequent days as required until WBCT is  $\leq 120\%$  of BL (based on the coagulometer) and  $\leq 110\%$  of BL (based on the manual method). Note that the differences in these thresholds is based on the differences in assay sensitivity between the two testing methods (Section 3.2.2). Once both WBCT thresholds have been met, no further WBCT testing is required.

Five days after ciraparantag/PBO dosing (Day 8 or Day 9), subjects may be discharged from the study unit, provided that the last (final) WBCT results are  $\leq 120\%$  of BL (based on the coagulometer) and  $\leq 110\%$  of BL (based on manual WBCT), and the Investigator determines that no additional safety monitoring is required. Otherwise the subject will remain domiciled until these criteria are met. The detailed schedule of study assessments is provided in [Appendix A](#).

An overview of the study design is provided in [Figure 1](#).

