### **3.3. Duration of Subject Participation**

Subjects will participate in the study for up to approximately 6 weeks. This will consist of a Screening period (up to 30 days) and a domiciled period in the study unit (up to 10 days).

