## **4. STUDY POPULATION**

### **4.1. Inclusion Criteria**

Eligible subjects must:

1. Be informed of the nature of the study and provide written informed consent before any study-specific procedures are performed.
2. Be 18 to 75 years of age, inclusive, at time of consent.
3. Be in good health, in the opinion of the Investigator, based on medical history, physical examination, vital signs, ECG and laboratory testing (ie, absence of any clinically relevant abnormality) during Screening.
4. Have a body mass index 18 to 32 kg/m^2, inclusive, at Screening.
5. If female, be surgically sterile or post-menopausal (no menses for at least 12 months), or if of child-bearing potential, must be using an acceptable method of contraception (other than a combination estrogen/progestin hormonal contraceptive) for at least 1 month prior to Day 1, such as an intrauterine device (IUD), implant, or two forms of the following: diaphragm, cervical cap, patch, condom, spermicide, or sponge. In addition, females of child-bearing potential must agree to continue to use their method of birth control for the duration of the study and 12 weeks following discharge from the study.
6. If male, be surgically sterile, or agree to use appropriate contraception (latex condom with spermicide) when engaging in sexual activity and agree to not donate sperm for the duration of the study and 12 weeks following discharge from the study.
7. Have suitable venous access for multiple venipunctures.

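### Pregnancy notification in Protocol Section 7.4 stops with the study, although contraception is required for 12 more weeks, so an uncomplicated pregnancy begun in those weeks need not be reported

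*Protocol*

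**What the plan says.** Three parts of the Protocol bear on this.

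- **Notification (Section 7.4).** The duty arises in this case: "Should a female subject or female partner of a male subject become pregnant at any time during the study". Then "the Investigator must notify the Sponsor within 24 hours after learning about the pregnancy", and the Sponsor asks for the course and outcome. No period after discharge is named.
- **Participation (Sections 3.1 and 3.3).** "Subjects will participate in the study for up to approximately 6 weeks", made up of Screening (up to 30 days) and the stay in the unit (up to 10 days). Dosed subjects "will remain domiciled in the clinical study unit for 5 days after dosing", that is, to Day 8 or Day 9.
- **Contraception (Section 4.1, criteria 5 and 6).** Women who could become pregnant "must agree to continue to use their method of birth control for the duration of the study and 12 weeks following discharge from the study". Men who are not surgically sterile must use contraception and "agree to not donate sperm for the duration of the study and 12 weeks following discharge from the study".

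The Schedule of Events places the last pregnancy test at FU-5. It lists no visit or contact after discharge.

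**The concern.** The Protocol asks subjects to avoid conception for 12 weeks after they leave the unit, but its notification rule does not follow them there. After dosing, the days that the rule does cover are spent in the unit, where conception is unlikely. The partner of a male subject is not domiciled, but he is.

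What is at stake is safety information. A pregnancy conceived in the 12 weeks after exposure, in a subject or a male subject's partner, could run its course without the Sponsor hearing of it. If only adverse outcomes were reported, the number of exposed pregnancies behind them would be unknown. No efficacy result is involved.

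**Working it through.** The check is calendar arithmetic, counted from the ciraparantag/placebo dose and assuming discharge on schedule at FU-5.

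**1. The plan's own duration figure.** Screening 30 days + unit stay 10 days = 40 days, and 40 / 7 = 5.7 weeks. This reproduces the approximately 6 weeks of Section 3.3. Adding 84 days would give 124 days, or 17.7 weeks, so the stated participation cannot include the 12 weeks.

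**2. The contraception period after dosing.**
- Dose to discharge: Day 3 to Day 8, or Day 4 to Day 9 = 5 days.
- After discharge: 12 × 7 = 84 days.
- Total: 5 + 84 = 89 days, ending on about Day 92 or Day 93.

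**3. The share covered by Section 7.4.**
- Covered: 5 / 89 = 5.6%.
- Not covered: 84 / 89 = 94.4%.
- Counted instead from the first anticoagulant dose: 7 / 91 = 7.7% (discharge on Day 8) or 8 / 92 = 8.7% (Day 9).

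**4. What the SAE rules add.** Section 7.3 carries all SAEs to 30 days after the last dose, and SAEs considered related beyond that with no end date.
- 30 / 89 = 33.7% of the period after dosing.
- Days after discharge: 30 − 5 = 25, and 25 / 84 = 29.8%.
- Remaining: 89 − 30 = 59 days, in which only related SAEs are reportable.

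**5. Coverage by type of event.** Columns show when the event falls.

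| Event | Consent to discharge | Next 25 days | Last 59 days |
|---|---|---|---|
| Start of an uncomplicated pregnancy | Notify Sponsor | No duty | No duty |
| Pregnancy-related SAE | Reportable | Reportable | Reportable if judged related |

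The first row rests on the statement in Section 7.4 that pregnancy in itself is not an AE, except where the product is suspected of interfering with contraception. AE monitoring in any case ends at FU-5 or discharge, whichever is later (Schedule of Events, note s).

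**6. A rough idea of the numbers.** The SAP limits analysis to Group 1 of Cohorts 1 and 3. At target that is 2 × 12 = 24 ciraparantag subjects. With 50% to 70% of randomized subjects aged 50 or over, 30% to 50% are younger: 7.2 to 12 subjects. If half of these are women (an assumption; sex balance is planned per cohort, not per age stratum or arm), that is about 4 to 6 women under 50. Partners of male subjects add to this, and the documents give no basis for an expected number of pregnancies.

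**The case against.** The strongest reply is that much of what matters already has a route. Section 7.4 makes spontaneous abortion an SAE and has complications and medical terminations recorded as an AE or SAE. Section 7.1.2 lists congenital anomaly in the child or fetus of an exposed female subject. Section 7.3 carries SAEs past discharge. A pregnancy that began during the study is followed to outcome, and Section 7.4 sets no cut-off on when the Investigator learns of it. All of this stands. A reader might infer from the mismatch that pregnancies after exposure are never collected, and the documents do not support that. The gap is narrower: uncomplicated pregnancies that begin after discharge, and later events not judged related.

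Four further points can be made.

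- *Section 7.4 does not define the study period, so a site could read it as the whole trial.* True, but Section 4.1 names the study and then adds 12 weeks following discharge, which treats those weeks as outside it. Section 3.3 agrees.
- *The notification window is not simply the time in the unit.* Correct. It includes up to 30 days of Screening at home, and so conceptions shortly before admission that might be missed on Day -1 and be present at dosing. FU-5 is a further chance to find them.
- *The 12 weeks are not described as a period of fetal risk.* Also correct. Calling them the risk window would be inference; they are the Protocol's own contraception period.
- *The consent form may already ask subjects to report later pregnancies.* It is a separate document, not seen here, so this cannot be judged.

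**Conclusion.** The point holds as a mismatch between two sections of the Protocol. Section 7.4 ties notification to the study, which for an individual ends about 5 days after ciraparantag/placebo, while criteria 5 and 6 run 12 weeks longer. On that reading 84 of 89 days after dosing carry no pregnancy-notification duty.

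The 94.4% is a share of calendar days. A reader might take it as the share of pregnancies missed, or as the share of days with no safety reporting at all. It is neither: contraception is mandatory, few subjects are concerned, and the SAE rules still apply in part.

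The conclusion assumes discharge on schedule and the individual-level reading of the study period. It takes the 12-week contraception period as given and does not judge its length. The point is minor: a cheap improvement in safety reporting with no effect on endpoints, alpha, power or analysis.

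**What to change.** Keep the start of the window in Section 7.4 and move its end, so that notification covers a pregnancy beginning at any time from informed consent until 12 weeks after discharge from the study. Starting the window at the first anticoagulant dose would be a step back, because it would drop conceptions between consent and Day 1 that the present wording covers.

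At discharge, ask each subject to report such a pregnancy, including a partner's, to the site. Put the same request in the consent form if it is not already there.

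The cost is a few lines of text and a small number of additional follow-up reports. No visit or test is added.

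Because the SAP states that the study was terminated, apply the change to any remaining follow-up and to later ciraparantag protocols. The study report should state that pregnancies in the 12 weeks after discharge were not systematically collected.

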## 8. CLINICAL TRIAL MATERIALS

### 8.1. Study Drug Supplies

#### 8.1.1. Ciraparantag and Placebo

Supplies of IV ciraparantag and the PBO comparator are described in Table 10.

**Table 10: Identity of Investigational Product**

Study Drug	Formulation
Ciraparantag for IV injection (supplied by the sponsor)	Each single-use clear vial contains 30.5 mL of sterile, isotonic, pH neutral solution for injection containing 6 mg/mL ciraparantag (10 mg/mL ciraparantag acetate) + 6.8 mg/mL sodium chloride.
Placebo for IV injection (supplied by the study site)	Sterile 0.9% Sodium Chloride Injection, USP.

#### 8.1.2. Anticoagulants

All anticoagulant drugs will be supplied by the sponsor. For use in the respective cohorts, the anticoagulant drugs will be provided as follows:

- Savaysa® (edoxaban; Daiichi Sankyo, Inc.): 60 mg tablets for oral administration
- Eliquis® (apixaban; Bristol-Myers Squibb): 5 mg tablets for oral administration
- Xarelto® (rivaroxaban; Janssen Pharmaceuticals, Inc): 20 mg tablets for oral administration

### 8.2. Packaging and Labeling

#### 8.2.1. Ciraparantag

Vials will be labeled for clinical study use with identifying information such as the lot number, storage conditions, and other details as appropriate.

### **8.2.2. Placebo**

The PBO in this study is sterile 0.9% Sodium Chloride Injection, USP, which will be provided by the study site in amounts needed to match the administered volume of ciraparantag at any given dose level.

### **8.2.3. Anticoagulants**

Each of the commercially available anticoagulant drugs (edoxaban, apixaban, or rivaroxaban) will be provided by the Sponsor for the respective cohort.

## **8.3. Storage and Accountability**

Study drugs provided to participating clinical sites will be stored, dispensed, and recorded in accordance with this protocol and the Pharmacy Manual. Only subjects enrolled in the study may receive study drug.

### **8.3.1. Storage**

Ciraparantag will be stored refrigerated at 2 to 8°C (36 to 46°F) and shipped on cold packs to the clinical test site. Temperature will be monitored during shipping for excursions. After arrival at the clinical study site, it will be refrigerated at 2 to 8°C (36 to 46°F) until prior to administration.

PBO (sterile 0.9% Sodium Chloride Injection, USP) will be provided by the study site and stored at room temperature prior to administration.

Anticoagulant drugs should be stored according to their prescribing information (i.e., product labels).

Drug supplies must be stored in a secure, limited-access location under the storage conditions specified on the label. Refer to the Pharmacy Manual for additional guidance on study drug storage.

### **8.3.2. Study Drug Accountability**

The Investigator or his/her designee will maintain accurate records of the receipt of all study drugs. In addition, accurate records will be kept regarding when and how much of each study drug is dispensed, used and unused by each study subject. Study center personnel should not dispose of any used or unused study drug until drug accountability is performed by the Sponsor or its designee. At the conclusion of the study, any unused study drug will be returned to the Sponsor or destroyed by the site pursuant to written authorization by the Sponsor and applicable federal and state regulations.

## **8.4. Preparation of Study Drug**

The study drugs must be prepared by qualified individuals, assigned by the Investigator.

The anticoagulant drugs will be administered in open-label fashion. Anticoagulant drug supplies can be handled by members of the study team who are qualified to store and dispense study drug.

An unblinded TAP will prepare the IV ciraparantag/PBO for each subject. The TAP must not be involved in the enrollment of subjects or in the performance or recording of any safety or efficacy assessments (including performance of any WBCT testing). Qualifications of the TAP and detailed instructions for the storage, handling, and preparation of study drugs will be provided in the Pharmacy Manual.

## **8.5. Point-of-Care Coagulometer**

The coagulometers to be used in this study are handheld devices supplied by Perosphere Technologies, Inc. that will provide an automated measurement of WBCT (Section 6.6.2). Each device uses single-use glass cuvettes onto which a small drop of blood is placed before insertion into the device. WBCT (based on fibrin clot formation) is measured using an infrared light beam; results are displayed on the device.

Instructions for use and maintenance of coagulometers are provided in a separate Procedures Manual. Study coagulometers will be returned to the Sponsor at the completion of the study. Specific instructions regarding return of coagulometers will be provided separately.

## **9. STATISTICAL PLAN**

### **9.1. Analysis Populations**

The Enrolled Population will include all subjects who remain eligible after the Day -1 assessments (ie, are not Screen failures) and are admitted to the study unit for the domiciled study period.

The Safety Population will include all randomized subjects who receive at least one dose of ciraparantag/PBO. Subjects will be analyzed based on the actual treatment they received. Full safety analyses will be performed on this population.

The Anticoagulant Population will include all subjects in the Enrolled Population who receive at least one dose of anticoagulant (edoxaban, apixaban, or rivaroxaban). Limited safety analyses will be performed on this population.

The Efficacy Population will include those randomized subjects who receive the planned single dose of ciraparantag/PBO and have at least one subsequent WBCT measurement. Subjects will be analyzed based on their randomized treatment assignment. Efficacy analyses will be performed on this population.

The PK Populations (separately for ciraparantag and each anticoagulant) will include all subjects who receive at least one administration of ciraparantag or anticoagulant, respectively, and provide sufficient data to estimate at least one PK parameter without any protocol deviations with the potential to affect these measurements. These populations will be used for PK analyses.

## **9.2. Study Endpoints**

### **9.2.1. Efficacy Endpoints**

For all endpoints listed below, analyses will be based on WBCT results obtained with the coagulometer unless otherwise specified.

#### **9.2.1.1. Primary Efficacy Endpoint**

The primary efficacy endpoint is achieving a WBCT  $\leq 120\%$  of BL within 1 hour after administration of ciraparantag/PBO, which is subsequently sustained after 1 hour through at least 6 hours after ciraparantag/PBO dosing.

#### **9.2.1.2. Secondary Efficacy Endpoints**

The secondary efficacy endpoints are as follows:

1. Achieving WBCT  $\leq 115\%$  of BL within 1 hour after administration of ciraparantag/PBO, which is subsequently sustained after 1 hour through at least 6 hours after ciraparantag/PBO dosing.
2. Achieving WBCT  $\leq 110\%$  of BL within 1 hour after administration of ciraparantag/PBO, which is subsequently sustained after 1 hour through at least 6 hours after ciraparantag/PBO dosing.
3. Achieving WBCT  $\leq 120\%$  of BL within 30 minutes after administration of ciraparantag/PBO, which is subsequently sustained after 30 minutes through at least 6 hours after ciraparantag/PBO dosing.
4. Achieving WBCT  $\leq 115\%$  of BL within 30 minutes after administration of ciraparantag/PBO, which is subsequently sustained after 30 minutes through at least 6 hours after ciraparantag/PBO dosing.
5. Achieving WBCT  $\leq 110\%$  of BL within 30 minutes after administration of ciraparantag/PBO, which is subsequently sustained after 30 minutes through at least 6 hours after ciraparantag/PBO dosing.
6. Achieving a WBCT  $\leq 120\%$  of BL within 15 minutes after administration of ciraparantag/PBO, which is subsequently sustained after 15 minutes through at least 6 hours after ciraparantag/PBO dosing.
7. Achieving a WBCT  $\leq 115\%$  of BL within 15 minutes after administration of ciraparantag/PBO, which is subsequently sustained after 15 minutes through at least 6 hours after ciraparantag/PBO dosing.
8. Achieving a WBCT  $\leq 110\%$  of BL within 15 minutes after administration of ciraparantag/PBO, which is subsequently sustained after 15 minutes through at least 6 hours after ciraparantag/PBO dosing.

